6.1.2 Standard Medical Treatment

Standard medical treatment will be administered per institution standards. Several guidelines are published for the management of complications and comorbidities of ACLF ([1,2,3,4,5](#)). Subjects will receive SMT (see [Section 2.1](#)) for the length of the study or as long as needed. Subject’s treatment period specified in this protocol will be 7 days for all subjects and will be prolonged, depending on subject’s ACLF evolution, to up to 17 days:

- Subjects in the SMT group with ACLF-1b, -2, or -3a who achieve complete response (ACLF resolution or improve to ACLF-1a) within the treatment period (from Day 1 to Day 7), will be assessed for 4 more days after the ACLF resolution or improvement and then will be followed up at Hospital Discharge (if applicable) and on Days 21, 28, 60, and 90.
- Subjects in the SMT group with ACLF-1b, -2, or -3a who maintain or worsen their ACLF grades throughout the treatment period (from Day 1 to Day 7), will be further assessed for up to Day 17 and will be then followed up at Hospital Discharge (if applicable) and on Days 21, 28, 60, and 90.

The entire follow-up period for subjects who receive SMT will be 90 days after randomization.

6.2 Prior and Concomitant Therapy

Prior (within 30 days prior to screening) and concomitant medications must be recorded in the eCRF and subject’s source documents, including the trade or generic name of the medication, the dose, the route of administration, and the duration and frequency of the medication.

Any medication administered during the study (including any blood products [including IVIG and SMT]) will be recorded on the eCRF and subject’s source documents with the

GRIFOLS
 
Bioscience Industrial Group
	
Number
 
BIG-CL-PRT-000002
 
IG1407 - Effects of Plasma Exchange with Human Serum Albumin 5% (PE-A 5%) on Short-term Survival in Subjects with "Acute-On-Chronic Liver Failure" (ACLF) at High Risk of Hospital Mortality
	
Version
 
6.0
	
Status
	
Retired
	
Effective Date
 
29-Mar-2023
	
Page
 
55 of 102

exception of anesthesia related products, fluid replacement therapies, and electrolyte supplementation. In addition, products administered at different doses on the same day to manage and maintain vital functions (eg, insulin, furosemide) will only be recorded once on the eCRF and subject’s source documents with the dosage reported as pro re nata.

In the event that an AE or suspected adverse drug reaction (ADR) should occur, complete details of all concomitant medication administered will be reported to the sponsor.

Usual treatments in decompensated cirrhosis will be allowed.

Treatment with terlipressin and albumin will be allowed in both treatment groups only in subjects developing type-1 hepatorenal syndrome (HRS) according to the International Club of Ascites (ICA) criteria (47). These subjects should follow the current EASL guidelines (48) in which management of type-1 HRS and indications of albumin are described. Noradrenalin plus albumin or the combination of octreotide, albumin and midodrine are considered a second line therapy of HRS. These treatments will be allowed in type-1 HRS only in countries where terlipressin is not available (United States of America [USA] and Canada).

6.2.1 Prohibited Medications Prior to Study Participation

Subjects receiving anti-platelet therapy or anti-coagulant therapy prior to enrollment (within 7 days prior to enrollment) cannot be included. In addition, subjects with HCV receiving antiviral therapy prior to enrollment cannot be included. Subjects antiviral therapy which was completed 14 days prior to randomization can be included in the study.

6.2.2 Prohibited Concomitant Medications during the Study

Use of the following medications is prohibited during the study participation.

During the treatment period (from Day 1 to Day 7, which could be prolonged to up to Day 17 depending on the clinical responses in the SMT+PE-A 5% treatment group or ACLF evolution in the SMT group), the administration of nephrotoxic (non-steroidal anti-inflammatory drugs, angiotensin II receptor antagonists, angiotensin converting enzyme inhibitors) or V2 receptor antagonists (Vaptans) will not be allowed. Oral β-blockers could be maintained in subjects receiving this treatment prior to enrolment. However, their replacement by IV somatostatin is recommended during the treatment period in subjects allocated to receive PE-A 5% in order to assure hemodynamic stability.

Albumin dialysis will not be allowed during the treatment period in the SMT+PE-A 5% group.

Bioartificial liver support systems are not considered SMT in ACLF. Therefore, this therapy will not be allowed in both treatment groups during the 90-day study period.

6.2.3 Restricted Concomitant Medications during the Study

This section describes medications that are restricted but not prohibited during the study participation:

GRIFOLS
 
Bioscience Industrial Group
	Number	BIG-CL-PRT-000002	Version	6.0	Status	Retired	Effective Date	29-Mar-2023
							Page	56 of 102
							IG1407 - Effects of Plasma Exchange with Human Serum Albumin 5% (PE-A 5%) on Short-term Survival in Subjects with "Acute-On-Chronic Liver Failure" (ACLF) at High Risk of Hospital Mortality	

Nephrotoxic drugs (Nonsteroidal anti-inflammatory drugs, aminoglycosides, colistin) may not be administered and should be restricted in subjects with infections by multiresistant bacteria unless there is no equivalent treatment available.

Platelet transfusion will be made in cases of severe thrombocytopenia (<20,000/mm³), or in the case of bleeding complications when the platelet count is below 50,000/mm³.

6.3 Treatment Compliance

Reasons for any deviation from the administration of less than 100% of the IP dose as prepared by the pharmacist, or designee, must be recorded in the eCRF and in the subject’s medical records.

7 ASSESSMENT OF EFFICACY

7.1 Efficacy Variables

Definitions

Diagnosis of cirrhosis will be established by histology or by clinical, analytical, and ultrasonographic findings. Organ failures will be defined according to the CANONIC Study criteria ([Table 2-1](#)). Liver failure: serum bilirubin ≥12.0 mg/dL; kidney failure: serum creatinine level ≥2.0 mg/dL or renal-replacement therapy; coagulation failure: International Normalized Ratio ≥2.5; cerebral failure: grade III or IV HE according to the West-Heaven criteria ([Appendix 9](#)) ([49](#)); circulatory failure: use of any vasopressor to maintain hemodynamic stability (the use of terlipressin for the treatment of HRS is not included in this definition); and respiratory failure: ratio of partial pressure of arterial oxygen to fraction of inspired oxygen (FIO₂) ≤200 or pulse oximetric saturation to FIO₂ ratio ≤214. Kidney dysfunction will be defined by a serum creatinine level ranging from 1.5 to 1.9 mg/dL. Mild-to-moderate HE will be defined by grade I or II HE.

ACLF-1a will be diagnosed in subjects with single kidney failure. ACLF-1b will be diagnosed in subjects with single organ failure with serum creatinine between 1.5 and 1.9 mg/dL and/or HE grade 1-2; ACLF-2 in the presence of 2 organ failures; and ACLF-3a in the presence of 3 organ failures, and ACLF-3b in the presence of 4 or more organ failures ([Table 2-1](#)). Complete response will be defined as resolution of ACLF or improvement to ACLF-1a and partial response as a reduction of 1 organ failure or more to ACLF-1b or ACLF-2.

Septic shock will be diagnosed in the presence of circulatory failure associated with inadequate oxygen utilization by the cells/inadequate tissue perfusion requiring vasopressor drugs. The presence of hypotension, although commonly present (MAP less than 60 to 65 mmHg), will not be required to define shock ([50](#)). Refractory septic shock will be diagnosed in subjects with high vasopressor requirements (norepinephrine dose >0.5 mcg/kg/min) ([51](#)). Diagnosis of ARDS will be established on the basis of a ratio PaO₂/FiO₂ ≤300 or a pulse oximetric saturation (SpO₂) to FiO₂ ratio ≤357 ([52](#)) add in the presence of bilateral lung infiltrates and normal left ventricular function.

Illness Severity Scores

The CLIF-C OF score, CLIF-C ACLF score, Child-Pugh score, and MELD score (Appendix 4) will be used to assess the clinical condition severity of the subjects.

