9.3.8 Organ Failure at the End of Hospitalization

Organ failure is defined according to the CANONIC study criteria for each of the following organs/systems: liver, kidney, brain, coagulation, circulatory, and respiratory. Kidney failure is defined as CLIF-C OF sub-score of 2 or 3; for all others, organ failure is defined as CLIF-C OF sub-score of 3. Refer to [Appendix 4](#) for additional details. The number and percentage of subjects experiencing organ failure will be summarized for each organ by visit, and at the end of hospitalization i.e. hospital discharge visit. The percentage of subjects with each organ failure at end of hospitalization will be compared between treatment groups using the Fisher’s Exact or Chi-square test.

Assessments after Liver transplant will be removed from summaries and analysis.

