Appendix 4 – Illness Severity Score Details

CLIF-Organ Failure score system.			
Organ / System	Sub-score = 1	Sub-score = 2	SUB-Score = 3
Liver	Bilirubin <6mg/dL	6 ≤ Bilirubin <12mg/dL	Bilirubin ≥12mg/dL
Kidney	Creatinine <2mg/dL	2 ≤ Creatinine <3.5 mg/dL	Creatinine ≥3.5 mg/dL or renal replacement
Brain (West-Haven grade for HE*)	Grade 0	Grade 1-2	Grade 3-4
Coagulation	INR <2.0	2.0 ≤ INR <2.5	INR ≥2.5
Circulatory	MAP ≥70 mm/Hg	MAP <70 mm/Hg	Use of vasopressors
Respiratory			
PaO ₂ /FiO ₂	>300	≤300 - >200	≤200 (#)
or			
SpO ₂ /FiO ₂	>357	>214 - ≤357	≤214 (#)

*The shaded area describes criteria for diagnosing organ failures; *HE: Hepatic Encephalopathy; # patients enrolled in the study with MV were considered as presenting respiratory failure (respiratory sub-score=3) except for patients intubated due to severe HE or to other reasons and not to a respiratory failure, in whom respiratory failure is defined according to the PaO₂/FiO₂ ratio. # Other patients enrolled in the study with MV were considered as presenting a respiratory failure (respiratory sub-score=3).*

CLIF-C ACLF Score

$$\text{CLIF-C ACLFs} = 10^{*}[0.33^{*}\text{CLIF-C OFs} + 0.04^{*}\text{Age \{years\}} + 0.63^{*}\text{Ln(white cell count \{10}^9 \text{ cells/L\})} - 2]$$

Child-Pugh Score

Child-Turcotte-Pugh Classification for Severity of Cirrhosis			
	Points*		
	1	2	3
Encephalopathy	None	Grade 1-2 (or precipitant induced)	Grade 3-4 (or chronic)
Ascites	None	Mild to moderate (diuretic responsive)	Severe (diuretic refractory)
Bilirubin (mg/dL)	< 2	2-3	>3
Albumin (g/dL)	> 3.5	2.8-3.5	<2.8
INR	<1.7	1.7-2.3	>2.3
*Child-Turcotte-Pugh Class obtained by adding score for each parameter (total points)			
Class A = 5 to 6 points (least severe liver disease)			
Class B = 7 to 9 points (moderately severe liver disease)			
Class C = 10 to 15 points (most severe liver disease)			

MELD Score

$$\text{MELD Score} = 9.57 \text{ Ln(Creatinine \{mg/dl\})} + 3.78 \text{ Ln(Bilirubin \{mg/dl\})} + 11.2 \text{ Ln(INR)} + 6.43$$

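### The SAP's circulatory-failure rule omits the protocol's exclusion of terlipressin given for hepatorenal syndrome, a gap already present in the protocol's own Appendix 4

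*Protocol*

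**What the plan says.** Protocol 7.1 gives the organ-failure definitions and their source: "Organ failures will be defined according to the CANONIC Study criteria". For the circulation it reads "circulatory failure: use of any vasopressor to maintain hemodynamic stability", qualified by "the use of terlipressin for the treatment of HRS is not included in this definition". The same section then says that the severity scores in Appendix 4, CLIF-C OF and CLIF-C ACLF among them, "will be used to assess the clinical condition severity of the subjects".

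Protocol Appendix 4, whose title presents it as the criteria for organ failure, gives circulatory sub-score 3 for vasopressor use without qualification. SAP Appendix 4 repeats that cell: "Use of vasopressors".

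SAP 9.3.8 names the same source as the protocol: "Organ failure is defined according to the CANONIC study criteria for each of the following organs/systems". It then converts sub-scores into failures. Kidney failure is sub-score 2 or 3, and "for all others, organ failure is defined as CLIF-C OF sub-score of 3".

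Protocol 6.2 makes the excluded use foreseeable: "Treatment with terlipressin and albumin will be allowed in both treatment groups only in subjects developing type-1 hepatorenal syndrome". For the USA and Canada, where it says terlipressin is not available, it allows regimens based on noradrenalin, or on octreotide with midodrine, for type-1 HRS.

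**The concern.** Two rules for one event stand in the plan, and the one the programmer will use is the one without the exclusion. SAP 9.3.8 does adjust the kidney sub-score so that it agrees with the creatinine threshold in protocol 7.1, but it does not carry over the circulatory exception. SAP section 12, which lists departures from the protocol, mentions no change to the organ-failure definition. This looks like an oversight, not a decision.

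At stake is the meaning of the circulatory row. Treatment of a renal complication could be tabulated as circulatory failure, and SAP 10.2, which counts HRS and organ failures in the same set of summaries, could show one HRS episode under both. If PE-A 5% changes how often type-1 HRS develops or is treated, the misclassification would differ between arms, and a renal effect could be read as a circulatory one.

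**Working it through.** The plan states no figure on this point to reproduce. The check sets the definitions side by side and then runs the plan's own score formulas.

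**1. The four places compared**

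| Place | Circulatory failure or sub-score 3 | Limited to haemodynamic support? | HRS terlipressin excluded? |
|---|---|---|---|
| Protocol 7.1 | vasopressor use | yes | yes |
| Protocol Appendix 4 | vasopressor use | no | no |
| SAP Appendix 4 | vasopressor use | no | no |
| SAP 9.3.8 | sub-score 3 | no | no |

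**2. One subject under each rule.** Take a subject whose only vasopressor is terlipressin for type-1 HRS. Under protocol 7.1 this is not circulatory failure. Under the SAP, exclusion criterion 6v3 in protocol 5.2 already treats terlipressin as a vasopressor, so a literal reading gives sub-score 3, and 9.3.8 makes sub-score 3 a failure. The organ-failure count differs by one.

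**3. Effect on the scores, if the exclusion is meant to reach the sub-score.** Without the vasopressor criterion, MAP sets the circulatory sub-score: 1 if MAP is at least 70, 2 if below 70 (both Appendix 4 tables). CLIF-C OF is the sum of six sub-scores (SAP 9.3.2). CLIF-C ACLF contains the term 10 × 0.33 × CLIF-C OF (SAP 9.3.3), that is 3.3 per point.

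- MAP at least 70: CLIF-C OF 3 − 1 = 2; CLIF-C ACLF 3.3 × 2 = 6.6.
- MAP below 70: CLIF-C OF 3 − 2 = 1; CLIF-C ACLF 3.3 × 1 = 3.3.

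**4. Illustration at arm level.** The share of affected subjects is not in the documents. The shares below are assumptions, applied to the planned 190 per arm. The study stopped early, so real counts may be smaller.

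| Assumed share | Extra circulatory failures | Mean CLIF-C OF shift | Mean CLIF-C ACLF shift |
|---|---|---|---|
| 5% | 190 × 0.05 = 9.5 | 0.05 to 0.10 | 0.17 to 0.33 |
| 10% | 190 × 0.10 = 19 | 0.10 to 0.20 | 0.33 to 0.66 |
| 20% | 190 × 0.20 = 38 | 0.20 to 0.40 | 0.66 to 1.32 |

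Each range runs from all affected subjects having MAP below 70 to all having MAP at least 70. The figures refer to a single visit.

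**5. Reach.** The organ-failure rule feeds the by-visit tables and the Fisher or chi-square comparison at hospital discharge (SAP 9.3.8), its adjusted sensitivity analysis (9.3.11) and the complications summary (10.2). The discharge comparison is touched only for subjects scored as on terlipressin at that visit. The sub-score and total-score models (9.3.2, 9.3.3) are touched only under the condition in step 3. The endpoints in SAP 9.1 and 9.2 are times to death or transplant, and their ACLF strata come from IWRS, so none of them uses this derivation.

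**The case against.** The strongest reply is that the SAP follows the protocol. Protocol 3.1.3 and 7.1.3 tie this endpoint to the CLIF-C OF score, protocol Appendix 4 defines that score without the exclusion, and the SAP copies the table. SAP 9.3.8 also cites the same CANONIC criteria that protocol 7.1 applies with the exclusion. Much of this stands: the conflict lies first between protocol 7.1 and protocol Appendix 4. It does not remove the problem, because the SAP states an explicit sub-score rule and that rule departs from the definition in 7.1.

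A reader might infer that the CLIF-C OF and CLIF-C ACLF totals in the SAP also depart from the protocol. The documents do not support that. Section 7.1 writes the exclusion into the organ-failure definition and refers the scores to Appendix 4, which the SAP matches.

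A reader might also infer that the error falls on one region, since terlipressin is described as unavailable in the USA and Canada. That does not follow. Noradrenalin, which protocol 6.2 allows there for type-1 HRS, would also score 3 on a literal reading. The exclusion names only terlipressin, and whether noradrenalin for HRS falls outside 7.1 because it is not haemodynamic support is left open. What the documents show is undefined handling, not a one-sided error.

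**Conclusion.** The point holds in a narrow form. Followed literally, SAP 9.3.8 classes terlipressin given only for HRS as circulatory failure, and protocol 7.1 does not. Per affected subject-visit the difference is one organ failure. It is also 2 or 1 points on CLIF-C OF and 6.6 or 3.3 on CLIF-C ACLF, but only if the exclusion is meant to reach the sub-score, which the documents do not settle.

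It would be too strong to say that organ failures are overstated. Sites score severity at each visit under a protocol that contains the exclusion and may already have applied it; neither their practice nor the frequency of terlipressin use is documented. Nor can a shift of one ACLF grade be asserted. SAP 9.3.7 works with the ACLF grade and gives no rule for deriving it from the sub-scores, and the protocol has the grade recorded separately at each visit. Course would change only if grades were derived from the unqualified table.

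Only exploratory and descriptive outputs outside the fixed testing sequence are involved. This is a minor point, worth settling because it is cheap.

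**What to change.** Reconcile protocol 7.1, protocol Appendix 4, SAP 9.3.8 and SAP Appendix 4, so that the SAP's organ-failure derivation matches the protocol definition. In doing so, state:

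- whether the exclusion applies only to the organ-failure definition or also to the CLIF-C OF circulatory sub-score, and so to both totals;
- how the other HRS regimens allowed in protocol 6.2 are handled. The present exclusion does not name them, and this review does not propose a rule for them;
- which eCRF data identify the subjects, for example the disease-related complications page, where HRS type is captured, read together with concomitant medications.

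Any change to Appendix 4 should be made in both documents; editing the SAP table alone would make its score differ from the protocol's. Because these definitions also underlie ACLF grade, and through it the number of PE sessions, the choice of definition belongs with the sponsor's clinical team.

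The cost is one extra derivation rule and some review of medication records, since indication is not among the medication fields listed in protocol 6.2. MAP is scheduled at every visit, so the sub-score can be re-derived where it was recorded. The survival analyses do not change.

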7.1.1 Primary Efficacy Variable

- The primary efficacy variable will be time to death through Day 90 after randomization of SMT+PE-A 5% versus SMT alone.

7.1.2 Secondary Efficacy Variables

- Time to transplant or death through Day 90 after randomization of SMT+PE-A 5% versus SMT alone.
- Time to death through Day 28 after randomization of SMT+PE-A 5% versus SMT alone.

7.1.3 Exploratory Efficacy Variables

- Time to death through Day 90, time to transplant or death through Day 90, and time to death through Day 28 after randomization in subgroups of subjects with ACLF-1b, ACLF-2, or ACLF-3a.
- Time to death and time to transplant or death through in-patient hospital stay (including ICU stay) in the entire study population and in the subgroups of subjects with ACLF-1b, ACLF-2, or ACLF-3a.
- Time to transplant or death through Day 28 after randomization in the entire study population and in the subgroups of subjects with ACLF-1b, ACLF-2, or ACLF-3a.
- Incidence of individual organ failures: liver, renal, brain, coagulation, circulation and respiration, as defined by the CLIF-C OF score and the total CLIF-C OF score, during the treatment period and at the end of treatment, and of hospitalization (or liver transplantation or death).
- ACLF course (resolution, improvement, steady course, or worsening), score, CLIF-C ACLF score, Child-Pugh score, and MELD score
- Systemic inflammation as measured by CRP, WBC, and procalcitonin
- Rate of all new infections.
- Time-to-hospital discharge.
- Albumin levels in serum measured pre and post PE-A 5% to monitor the status of infused albumin in subjects during the course of the study.

7.2 Methods and Timing for Assessing, Recording, and Analyzing Efficacy Parameters

7.2.1 Observations and Measurements

The following is a description of the procedures/assessments to take place at each study visit. See the Schedules of Study Procedures and Events in [Appendix 1](#) and [Appendix 2](#) for summaries of study visits and the procedures to be conducted at each visit.

7.2.1.1 Screening Period (Day -10 to Day -1)

Following signature of the informed consent form (ICF), screening procedures will be performed. If a subject is ineligible for participation, their demographic data and specific reason for ineligibility will be captured on the subject’s source documents and eCRF.

The Screening Period assessments and activities will include:

- Assign subject number
- Add subject’s data into the Screening Log
- Review of inclusion and exclusion criteria (see [Sections 5.1](#) and [5.2](#), respectively) to determine subject’s eligibility
- Documentation of demographics: year of birth, gender, race, and ethnic origin
- Documentation of medical history, including etiology of cirrhosis and significant concomitant disease conditions for the last 12 months
- Chest x-ray
- Electrocardiogram (ECG)
- Abdominal ultrasound
- Urine pregnancy test (human chorionic gonadotrophin [HCG]-based urine assay) for women of childbearing potential (to be performed locally at the investigative study center)
 - Women of child-bearing potential include any female who has experienced menarche and who has not undergone successful surgical sterilization (hysterectomy, bilateral tubal ligation or bilateral oophorectomy) or is not postmenopausal (postmenopausal is defined as amenorrhea for more than 12 consecutive months or women on hormone replacement therapy with documented serum follicle stimulating hormone level <35 mIU/mL). Women who are using oral, implanted, or injectable contraceptive hormones or mechanical products such as an intrauterine device or barrier methods to prevent pregnancy or practicing abstinence or where their sexual partner is sterile (eg, vasectomy), should be considered to be of child-bearing potential.
- Full physical examination (excluding breast and genitourinary examination)
- Record vital signs (systolic blood pressure [SBP], diastolic blood pressure [DBP], HR, respiratory rate [RR], temperature [T])

- Ascites assessment according to the ICA criteria ([Appendix 10](#))
- Record weight
- HE assessment ([Appendix 9](#))
- Hemodynamics assessment (mean arterial pressure [MAP])
- Peripheral oxygen saturation (SpO₂) assessment
- Blood sample collection for clinical laboratory assessments (eg, hematology, chemistry, coagulation)
- Infection surveillance using microbiology (cultures) including blood, urine, ascetic fluid, sputum, and pleural fluid. If a positive result occurs at screening, a Day 3 result will be collected. If a thoracentesis or paracentesis has been performed within the last 5 days prior to screening, results of the fluid cultures should be documented in the medical notes. Microbiology cultures will be performed at local labs and the results will be captured in the subject's source documents but will not be entered into the eCRF. All new infections will be recorded as AEs and recorded in subject's source documents and the eCRF. Additional samples will be obtained upon clinical suspicion.
- Microbiological tests (Cytomegalovirus [CMV] polymerase chain reaction [PCR], and galactomannan antigen index)
- Record ACLF grade ([Table 2-1](#))
- Illness severity scores: CLIF-C OF score, CLIF-C ACLF score, Child-Pugh score, and MELD score ([Appendix 4](#))
- Blood biomarker retains for subjects in the SMT and SMT+PE-A 5% groups
- Record prior (30 days prior to screening) and concomitant medications
- Record AEs

Subjects with ACLF-1b, ACLF-2, or ACLF-3a will be included at diagnosis of the syndrome. Subjects with ACLF-1a will be followed up and included if they deteriorate to ACLF-1b, ACLF-2, or ACLF-3a within the 10-day Screening Period. Subjects with ACLF-3b will be followed up and included if they improve to ACLF-3a, ACLF-2, or ACLF-1b within the 10-day Screening Period.

Evaluation of cardiac function at screening will be optional in subjects without vascular failure but mandatory in those with shock. This evaluation will be performed according to local guidelines.

